8.2 Procedures

Our study will follow the design outlined above (section 5.1).

There is no informed consent needed for the use of this data. There will be no participant recruitment or compensation. Potential risks and benefits of the study are reported elsewhere (section 11.6).

Two CRCs will be hired to analyze de-identified patient data. CRCs will access the data via a password-protected portal, using a UPHS desktop and/or laptop. De-identified patient chart data will be included for analysis based on having a tumor type of interest. They will then review patient charts and record clinical elements of interest in the Mendel abstraction tool, which will be secured in a HIPAA-compliant external enclave. Summary-level data will be exported into datasheets for analysis. These datasheets will only be used and analyzed on UPHS equipment, or shared via HIPAA-compliant means.

Data will be analyzed using statistical software including Excel, R code, and STATA. For details of the analysis plan, see section 9.

Data elements that will be abstracted across all arms of the study include the following (the below list may change slightly pending further discussion among the research team):

Cancer Type and Staging

- Cancer Type
- Stage - Tumor
- Stage - Node
- Stage - Mets

Performance

- ECOG Performance Status

Prior Systemic Treatment

- Any Prior Platinum Therapy (e.g., Cisplatin, Carboplatin, Oxaliplatin)
- Any Other Prior Chemotherapy (e.g., 5-fluorouracil, Leucovorin, Capecitabine, Irinotecan, Pemetrexed, Paclitaxel, Docetaxel, Gemcitabine)
- Any Prior Immunotherapy (e.g., Atezolizumab, Nivolumab, Pembrolizumab)

Biomarkers for CRC

- KRAS
- MSI-H
- MSS
- BRAF
- HER2
- NTRK
- DPYD

Biomarkers for NSCLC

- EGFR
- ALK
- ROS1
- KRAS
- BRAF
- NTRK
- cMET
- RET
- PDL1

Others

- Outcomes (remission, residual disease, recurrence, loco-regional recurrence, distant recurrence)
- Responses (complete response, stable disease, partial response, mixed response, disease progression)

9. Analysis plan

The primary study will be powered on a retrospective paired, non-inferiority design to evaluate abstraction accuracy of elements commonly used to help screen patients for clinical trials. The two arms are (1) human reviewers versus (2) human reviewers utilizing predictions from Mendel AI. The primary outcome, the percentage of gold standard items correctly abstracted, will be measured for each chart. Noninferiority can be established by comparing the difference in the

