mean proportion correct between the human-augmented and Human-alone arms with a predefined non-inferiority margin, Δ .

The one-sided hypotheses to test noninferiority of average chart-level accuracy of a Human+AI abstraction approach, compared with a Human-alone approach are outlined below:

$$H_0: \mu_{h-ai} - \mu_h \leq -\Delta \text{ (Null hypothesis)}$$

$$H_a: \mu_{h-ai} - \mu_h > -\Delta \text{ (Alternative hypothesis)}$$

Test statistic:

$$T_n = \frac{(\mu_{h-ai} - \mu_h) + \Delta}{\sqrt{\frac{Var(D)}{n}}}$$

Sample size equation for a noninferiority, paired study design:

$$n = \frac{(z_{1-\beta} + z_{1-\alpha})^2 \sigma^2}{((\mu_{h-ai} - \mu_h) + \Delta)^2} = \frac{(z_{1-\beta} + z_{1-\alpha})^2 \sigma^2}{(D + \Delta)^2}$$

As a secondary analysis, we will test the superiority of the Human+AI arm for achieving greater average chart-level accuracy, compared with the Human-alone arm. Our hypotheses are:

$$H_0: \mu_{h-ai} \leq \mu_h \text{ (Null hypothesis)}$$

$$H_a: \mu_{h-ai} > \mu_h \text{ (Alternative hypothesis)}$$

Sample size equation for a superiority, paired study design:

$$n = \frac{(z_{1-\beta} + z_{1-\alpha})^2 Var(D)}{(\mu_{h-ai} - \mu_h)^2}$$

Parameter	Description
μ_{h-ai}	Mean proportion of criteria correctly abstracted by AI-augmented human reviewers
μ_h	Mean proportion of criteria correctly abstracted by Human-alone reviewers
$D = \mu_{h-ai} - \mu_h$	Mean difference in chart-level accuracy between arms
Δ	Non-inferiority margin, set as 0.05 for conservative sample size estimates.
$z_{1-\beta}$	Critical value at $1-\beta$, where $1-\beta$ represents the desired power and β represents Type II error

$Z_{1-\alpha}$	Critical value at $1-\alpha$, where α = Type I error
σ^2	$n^* \text{Var}(D)$, where n is the sample size and $\text{Var}(D)$ is the variance of the mean difference in chart-level accuracy

*Note: μ_{h-ai} , μ_h , $\Delta > 0$.

From our initial calculations, 400 individual patients will achieve an estimated statistical power greater than 90% for this non-inferiority study with a Type I error of 5%. This was determined from simulations for different realistic parameter scenarios for TNR, event rate, and concordance assumptions showing that the needed sample size rarely exceeded 400.

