The goals of the secondary analyses are to compare the efficiency of screening among the three study arms. We will analyze efficiency, defined by comparing the average number of minutes per chart review, measured for each chart. A nonparametric, paired Wilcoxon Rank Sum test with continuity correction will compare overall median efficiency of chart abstraction between arms.

The following are post-hoc analyses to be conducted after the pre-specified main analyses. Superiority of chart-level accuracy for the Human+AI arm relative to Human-alone will be tested using a one-sided paired t-test with an unspecified inferiority margin. A sensitivity analysis will repeat the primary chart-level accuracy outcome analysis with a less strict definition of an accurate match to the gold standard set. To assess whether there is a difference in accuracy among the 12 trial eligibility criteria, criterion-level accuracy will be compared assessed between arms. To assess criterion-level accuracy, a two-sided, paired t-test will be conducted with Bonferroni correction for multiple hypotheses (i.e., $\alpha = 0.05 / n$, where $n=12$ was the number of criteria studied). For any criterion with a statistically significant difference in mean criterion-level accuracy, superiority of the Human+AI arm for criterion-level abstraction will be then assessed with an additional one-sided hypothesis with an unspecified superiority margin. Lastly, we repeat both the chart-level accuracy analysis and efficiency analyses while stratifying by chart characteristics that include chart complexity, length, order, and cancer type.

Descriptive statistics, including means, medians, proportions, and ranges, will be used to summarize each analyses. All statistical analyses will be conducted using appropriate statistical software, and will rely on a predetermined significance level (e.g., $\alpha = 0.05$). Effect sizes and confidence intervals will be reported where applicable to provide further context to the findings.

10. Investigators

[name], PhD (Principal Investigator) is [name] and [name] University Professor in Health Policy and Medical Ethics and Co-Director of the Healthcare Transformation Institute.

[name], MPP (Sub-Investigator) is Assistant Professor of Health Policy and Medicine and Innovation Faculty at the Penn Center for Cancer Care Innovation (PC3I).

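### Effects by chart complexity, length, order and cancer type are examined only by repeating the main tests within strata, with no interaction estimate or test

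*Combined protocol and SAP*

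**What the plan says.** Section 9 (Analysis plan) sets the primary analysis up as a "retrospective paired, non-inferiority design". It states "The one-sided hypotheses to test noninferiority of average chart-level accuracy", with the margin described as "Non-inferiority margin, set as 0.05 for conservative sample size estimates". Efficiency, in minutes per chart, is compared between arms with a paired Wilcoxon test.

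The sample size statement concerns the whole sample: "400 individual patients will achieve an estimated statistical power greater than 90" percent, at a Type I error of 5%. Its support is "simulations for different realistic parameter scenarios for TNR, event rate, and concordance assumptions showing that the needed sample size rarely exceeded 400". No values are given for those parameters, for the SD of the paired difference or for the assumed true difference.

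Section 9 then lists analyses that it labels post-hoc. The last of them reads: "we repeat both the chart-level accuracy analysis and efficiency analyses while stratifying by chart characteristics that include chart complexity, length, order, and cancer type". The section adds that all analyses rely on a predetermined significance level, and that effect sizes and confidence intervals will be given where applicable. Bonferroni correction is specified for the 12 criterion-level tests. No multiplicity rule is stated for the strata.

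The document gives no cut-points, number of levels or stratum sizes for complexity, length or order. Cancer type has two levels under section 5.5. No interaction or heterogeneity analysis appears anywhere.

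**The concern.** The natural reason to stratify is to learn whether AI assistance works differently on, for example, long charts and short ones. Separate tests in each stratum do not answer that. Each asks whether one stratum, on its own smaller sample, clears the 0.05 margin or shows a time difference. None compares the effect in one stratum with the effect in another.

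A stratum can miss the margin because the effect is worse there, or only because it holds fewer charts. The 400 charts were sized for the overall comparison, and no power is stated for any stratum. A mixed pattern of passes and misses would be easy to over-read as a finding about a type of chart, and the plan provides no estimate that would check that reading.

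**Working it through.** **Inputs from section 9:** n = 400 paired charts, margin 0.05, one-sided alpha 0.05 (z = 1.645), power above 90% (z = 1.282 at 90%).

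**Assumed:** SD of the per-chart paired difference, stratum sizes, and true difference D = 0 in every stratum.

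**Step 1: the plan's own figure.** The plan's formula is n = (z_power + z_alpha)² × SD² / (D + margin)². Without SD and D, the 400 cannot be reproduced. Inverting it gives the largest SD that still yields 90% power at 400 charts:

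SD = (D + 0.05) × √400 / (1.282 + 1.645)

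At D = 0 this is 1 / 2.927 = 0.342. It would be 0.205 at D = −0.02 and 0.478 at D = +0.02. The values 0.15, 0.20 and 0.342 are used below as a range.

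**Step 2: power within a stratum.** Power = Φ(0.05 × √n_s / SD − 1.645). For example, with n_s = 200 and SD 0.342: 0.7071 / 0.342 − 1.645 = 0.42, and Φ(0.42) = 0.66.

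| SD | n_s = 200 | n_s = 100 |
|---|---|---|
| 0.15 | 0.999 | 0.954 |
| 0.20 | 0.971 | 0.804 |
| 0.342 | 0.664 | 0.428 |

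**Step 3: chance that at least one of k equal strata misses non-inferiority, with the arms equal in all of them.** This is 1 − power^k. The strata of a single characteristic hold different charts, so their results are treated as independent.

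| SD | Two strata of 200 | Four strata of 100 |
|---|---|---|
| 0.15 | 0.2% | 17% |
| 0.20 | 6% | 58% |
| 0.342 | 56% | 97% |

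For example, 1 − 0.664² = 0.559 and 1 − 0.804⁴ = 0.58.

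**Step 4: one stratum passes and the other misses, with no true heterogeneity.** For a 300/100 split the chance is p₃₀₀(1 − p₁₀₀) + (1 − p₃₀₀)p₁₀₀. At SD 0.342 this is 0.813 × 0.572 + 0.187 × 0.428 = 0.545. It is 0.198 at SD 0.20 and 0.046 at SD 0.15.

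**Step 5: what an interaction test would offer.** For two strata of 200, the SE of the difference in effect is SD × √(1/200 + 1/200) = 0.1 × SD. The test is two-sided at 0.05.

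| SD | SE | Power for a 5-point difference in effect | Difference detectable with 80% power |
|---|---|---|---|
| 0.15 | 0.015 | 92% | 4.2 points |
| 0.20 | 0.020 | 0.705 | 5.6 points |
| 0.342 | 0.034 | 31% | 9.6 points |

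The interaction test holds a false claim of heterogeneity at 5% per test, whatever the SD. Pass/miss comparisons do not.

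No corresponding figure is given for efficiency, because the document gives no distribution for review time.

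**The case against.** The strongest reply is that the plan never says how stratum results will be interpreted. A reader might infer that effect differences will be judged by which strata pass, or that a missed stratum will be reported as loss of non-inferiority. The text contains no such rule. It labels these analyses post-hoc and promises confidence intervals where applicable. This stands, and the point should not be put as though the misreading were planned.

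A reader might also infer that the strata are underpowered. That is not established. Cancer type, the only characteristic whose levels the document defines, has two. With two equal strata and an SD of 0.15 to 0.20, each stratum has at least 97% power at D = 0. The plan also says that the simulated requirement seldom went above 400, so an SD near 0.342 is toward the unfavourable end. This stands too, and is why only a range can be given.

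A third tempting reading is that uncorrected stratum tests inflate false positives: 16 tests (four characteristics, two levels, two outcomes) would give 1 − 0.95¹⁶ = 56% if independent. That should carry no weight. The four characteristics cut the same charts, so the tests are not independent. For non-inferiority, a false positive at the 5% rate requires the AI-assisted arm to be worse by exactly 5 points, which is the opposite error from missing non-inferiority when the arms are equal. Correcting the stratum tests would worsen the latter: at n = 100, SD 0.20 and D = 0, dividing alpha by 8 lowers power from 80% to 50%.

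None of this answers the remaining point: as written, the plan has no analysis that estimates how the effect varies.

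**Conclusion.** The concern holds in a limited form. The stratified analyses cannot show whether the effect of AI assistance differs by chart type, because nothing planned compares the effects between strata. How often chance alone would produce a missed stratum depends on quantities the document does not give. Under equal arms, normal approximations and equal strata, the range is 0.2% to 56% for two strata and 17% to 97% for four, across SDs of 0.15 to 0.342.

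This is a minor point about exploratory analyses. The primary non-inferiority conclusion rests on the whole sample and is unaffected. The document does not support a claim that the plan will declare AI assistance inadequate for some type of chart.

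**What to change.** Amend the stratified-analysis sentence in section 9 as follows.

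- Define each characteristic and its levels. Report stratum estimates with 95% confidence intervals, and give no stratum-level non-inferiority verdicts.
- Add one arm-by-characteristic interaction estimate, with confidence interval and test, for each characteristic and outcome.
- For complexity, length (as a continuous variable) and cancer type, regress the paired accuracy difference on the characteristic. Do the same for the paired difference in log minutes, as a supplement to the Wilcoxon analysis and not a replacement for it.
- For order, use a read-level mixed model with a chart random effect and an arm-by-order term. Section 5.1 randomizes review order with manual and assisted reviews mixed, so a chart's two reads can fall at different positions and order cannot simply be regressed on the paired difference.
- Label all of these exploratory and not adjusted for multiplicity. Four characteristics by two outcomes make eight interaction tests, with a 1 − 0.95⁸ = 34% chance of at least one false positive if they were independent.

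The cost is a few regressions, provided that the chart characteristics and each read's position are recorded. The downside is that there are no stratum verdicts and that interaction power is limited (step 5 of the working), so a null interaction should not be read as proof of a uniform effect.

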11.1 Data confidentiality

Computer-based files will only be made available to personnel involved in the study through the use of access privileges and passwords. All identifiers will be removed from study-related information. Precautions will be put in place to ensure the data are secure by using passwords and HIPAA-compliant encryption. All patient data provided by Mendel.ai will be viewed by HIPAA-certified Research Coordinators trained in EHR screening within a secure enclave.

NOTE: No Penn data will be utilized in this study.

11.4 Data disclosure

The results of the study will be presented in aggregate form, with no disclosure of individual-level data. No information that identifies specific patients will be recorded as part of documenting and/or publishing the results of this research.

11.5 Data safety and monitoring

The investigators will provide oversight for the study evaluation of this project.

11.6 Risk/benefit

11.6.1 Potential study risks

The potential risks associated with this study are minimal given the research is focused on de-identified data from patient charts. Breach of data is a potential risk that will be mitigated by using HIPAA compliant and secure data platforms for analysis.

NOTE: No Penn data will be utilized in this study.

11.6.2 Potential study benefits

This is highly practical research because it assesses the effectiveness of AI-led and human-AI-assisted chart review for clinical trial eligibility screening. This has major implications for clinical research, as it could lead to significant time savings in screening patients for eligibility and ultimately lead to more cancer patients participating in clinical trials.

11.6.3 Risk/benefit assessment

The risk/benefit ratio is favorable given the potential benefit for significant practical knowledge that could be gained from understanding the potential for AI to review “unstructured” patient data and accelerate the process of identifying patient eligibility for clinical trials. Efforts have been put into place to minimize the risk of breach of data. If favorable outcomes are found, then there is a potential to leverage the insights to guide further research and future clinical practice.
